#### 4.1.4 Exploratory Endpoints

Any comparisons across timepoints (baseline to 6 months) not described in the primary or secondary endpoints, including but not limited to:

- Demographics:
  - o Male vs Female
  - Age  $\leq$ 50 years vs > 50 years
- Medical History
  - With / without history of joint surgery
- History of joint osteoarthritis
  - With / without prior joint pathologies
- Injection procedure:
  - With / without guidance
- Concomitant medications
- Non-drug therapy
  - o With / without non-drug therapy

Specifically, subset populations will be compared based on the primary endpoint result and OMAREACT OARSI responder index at 6 months for each subset.

For the exploratory analyses, the continuous variables will be summarized via descriptive statistics (n, mean, median, standard deviation, minimum, and maximum. The discrete variables will be summarized via counts and percents.

#### 4.2 STATISTICAL METHODS

Tabulation of summary statistics, graphical presentations, and statistical analyses will be performed using SAS® software 9.4 or higher version. Where not otherwise specified, the last pretreatment observation will be used as baseline for calculating post-treatment changes from baseline. The primary presentations and analyses will be based on data pooled across study centers. Relevant summaries for individual centers, or combinations of centers, may be presented for primary data. All testing and confidence intervals will use a significance level of 5%.

#### 4.3 DEMOGRAPHIC AND BASELINE CHARACTERISTICS

All demographic and baseline characteristics will be tabulated by treatment group and a test of homogeneity between the treatment groups will be conducted. For continuous variables (e.g. age, height, weight) a one way ANOVA will be used. For categorical variables (e.g. gender, race), a Fisher's exact test or chi-squared test will be used. Medical history findings, physical examinations and concomitant medications will be tabulated by treatment group.

The baseline, Vital Signs, and BMI data will be summarized via descriptive statistics and tested for homogeneity using a one way ANOVA.

#### 4.4 ADVERSE EVENTS

All AEs will be coded according to MedDRA. Safety assessments will include Treatment-Emergent Adverse Events (TEAEs) which are defined as AEs with an Investigator assessment of definitely, probably, or possibly related to CTM. TEAEs will be summarized with frequencies and percentages by system organ class and preferred term, severity, and relationship to study CTM for each treatment group. In summaries of TEAEs by severity and relationship to CTM for subjects reporting multiple episodes, all reported events will be included, not only the worst reported case. Serious Adverse Events will also be presented by relationship to the CTM.

The number of subjects with at least one AE will be tabulated for each treatment group. Differences between the treatment groups will be tested using Fisher's exact test. Then the number of AEs for each treatment group will also be tabulated.

The number of subjects and the number of AEs will be tabulated by severity, relationship, and local injection site specific events versus non local events.

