9.2.2 Adverse Events

Subjects with AEs will be summarized with frequencies and percentages by system organ class and preferred term, severity, and relationship to investigational product/procedure. In summaries of AEs by severity and relationship to investigational product/procedure, subjects reporting multiple episodes will be counted once under the worst severity and the strongest relationship, respectively. Serious Adverse Events will also be presented by relationship to investigational product/procedure.

Adverse events occurring prior to the index treatment will not be recorded in this trial.

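### SAP 4.4 gives its only system organ class/preferred term table for adverse events judged related, while Protocol 9.2.2 specifies that table for all adverse events

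*SAP*

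**What the plan says.** SAP 4.4 makes TEAE status depend on the investigator's causality assessment: "which are defined as AEs with an Investigator assessment of definitely, probably, or possibly related to CTM". It continues: "TEAEs will be summarized with frequencies and percentages by system organ class and preferred term, severity, and relationship to study CTM". For TEAE summaries by severity and relationship, where a subject has several episodes, "all reported events will be included, not only the worst reported case".

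For AEs of any cause, the same section plans the number of subjects with at least one AE, the number of AEs, and a further breakdown: "The number of subjects and the number of AEs will be tabulated by severity, relationship", with a split into local and non-local events. Serious AEs are shown by relationship. All AEs are to be coded in MedDRA.

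Protocol 9.2.2 starts from a different set of events: "Subjects with AEs will be summarized with frequencies and percentages by system organ class and preferred term, severity, and relationship to investigational product/procedure". In its severity and relationship summaries, "subjects reporting multiple episodes will be counted once under the worst severity and the strongest relationship, respectively". It adds: "Adverse events occurring prior to the index treatment will not be recorded in this trial". Protocol 8.1.1 has AEs recorded whatever their severity or relationship. The safety endpoint, in Protocol 6.4 and again in SAP 3.0, covers all AEs.

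**The concern.** The class/term table is where a reader learns which kinds of event occurred. Under the SAP, an event enters that table only if the investigator judged it at least possibly related. Protocol 6.5 describes an open-label study meant to evaluate residual risk, and there is one treated group. The event-type summary would therefore be filtered by a causality judgement made with knowledge of treatment, and there is no comparison group against which to check that judgement. An event type that investigators tended to call unrelated would not show up as a pattern in any specified table.

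The counting rules also differ. A reader who expects the protocol's rule would take each entry in a severity table to be one subject. The SAP's TEAE entries are episodes.

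**Working it through.** There is no plan figure to reproduce. The check is a comparison of text.

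1. **Which events enter the class/term table.** Protocol 9.2.2: subjects with AEs, with no causality condition. SAP 4.4: TEAEs, which by its definition are AEs judged at least possibly related. The SAP set is the protocol set minus AEs judged unrelated.

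2. **Whether the TEAE definition does any work on timing.** Protocol 8.1.1 records AEs during or after injection, and Protocol 9.2.2 rules out recording earlier ones. Every recorded AE therefore already has its onset at or after treatment. The SAP's condition does not sort events by timing. It only removes those judged unrelated.

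3. **Whether unrelated AEs reach a class/term table by another route.** The all-AE summaries in SAP 4.4 are subjects with any AE, number of AEs, severity, relationship, and local versus non-local. None is by class or term. The serious-AE summary is by relationship. SAP 1.0 promises data listings, but a listing is not the table of frequencies and percentages that Protocol 9.2.2 describes. No other SAP section specifies an all-AE class/term table.

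4. **Whether a departure is declared.** SAP 4.1 presents the SAP as the detail behind the protocol's analysis. It neither mentions nor justifies a change to the AE summaries. The protocol's change history (Appendix 4) lists only eligibility criteria, so no listed amendment explains the difference.

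5. **Counting rule.** Protocol 9.2.2, AE summaries: one entry per subject, at worst severity and at strongest relationship. SAP 4.4, TEAE summaries by severity and relationship: every episode. SAP 4.4, all AEs: both subjects and events are planned, but it does not say where a subject with several episodes is placed. The SAP also does not say whether TEAE percentages are of subjects or of events.

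6. **Relationship to what.** The protocol relates events to product or procedure. The SAP relates them to CTM, which neither the SAP text nor the protocol's abbreviation list expands. If CTM means the product alone, an event attributed only to the injection procedure would not be a TEAE and would also miss the class/term table. Protocol 4.2 lists such procedural risks.

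7. **Illustration with assumed data.** One subject has two mild related events, one severe related event and one unrelated event, 2 + 1 + 1 = 4 in all.
   - Protocol 9.2.2: the class/term summary covers the terms of all 4 events, and the severity summary counts the subject once, under severe.
   - SAP 4.4: the class/term summary covers the 3 related events, the TEAE severity summary holds 3 entries (2 mild, 1 severe), and the unrelated event appears only in the all-AE counts.

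**The case against.** The strongest reply is that nothing has been taken away. SAP 4.4 introduces TEAEs with inclusive wording, SAP 4.1 says the SAP details the protocol's analysis, and the protocol's table is nowhere withdrawn. All AEs are recorded and coded, so the table could be produced at reporting with no new data. In a study planned for about 25 subjects, listings would let a reader see every event. This stands in part. A reader might infer that the SAP drops unrelated AEs from safety reporting or cancels the protocol's table. The documents support neither reading: unrelated AEs stay in several planned counts, and the SAP is silent about the protocol's table. The omission itself remains, because a programmer working from SAP 4.4 would produce the related-only table and no other by class and term.

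On counting, the protocol never uses the term TEAE, and the SAP's all-episodes rule is written only for TEAE summaries. A reader might infer that the SAP overturns the count-once rule for all AE summaries. It does not. Subject counts for all AEs remain planned, and the protocol's rule could fill the gap. Showing every episode is also a legitimate display if it is labelled as event counts. Even so, TEAEs as defined are a subset of AEs, so the two rules give different entries for the same related events, and the SAP does not explain why.

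**Conclusion.** The SAP's AE section is wrong as written, and the correction is minor. The only class/term summary it specifies is conditional on an open-label relatedness judgement, whereas Protocol 9.2.2 and the safety endpoint call for all AEs. The counting mismatch is secondary and confined to TEAE severity and relationship summaries, together with an unstated multiple-episode rule for all AEs.

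The practical effect is one descriptive table missing from the SAP and one counting rule to reconcile. How many events are affected depends on AE and relatedness rates, which the documents do not give, so no figure can be attached. The conclusion rests on the text alone. It assumes that the SAP will be followed literally and that no table shells outside these documents already include an all-AE class/term table.

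**What to change.** In SAP 4.4:

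- Remove the relatedness condition from the TEAE definition. Recording starts at injection, so every recorded AE then qualifies.
- Specify the class/term table for all AEs in the Safety Population, with related AEs as a second table.
- In subject-level severity and relationship summaries, count each subject once as Protocol 9.2.2 does. Show event counts separately and label them as events.
- Express relationship in the protocol's terms, product or procedure, in place of CTM.

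The cost is SAP wording and one extra table. The AEs are already to be recorded whatever their relationship and coded in MedDRA, so no new data collection is needed.

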3. INTRODUCTION

MONOVISC® is Anika's next generation sodium hyaluronate device for treating joint pain. It has been designed to deliver comparable benefits to those of ORTHOVISC® with a single injection.

MONOVISC has previously shown clinical improvement when studied for osteoarthritis of knees. The MONOVISC 07-02 results show MONOVISC achieved a 44% improvement from baseline in WOMAC A scores.

Hyaluronic Acid injections in non-knee synovial joints has been reported to show benefits in pain reduction and improvement in joint function. Patients with hip osteoarthritis had significantly improved Lequesne's function and reduced VAS pain at 3 and 6 months after injection (Migliore et al. *Arthritis Research & Therapy* 2009 Vol 11 No 6). A study on the use of intra-articular HA in the treatment of symptomatic osteoarthritis of the shoulder showed an improvement in VAS score of 24 points from baseline to 6-months (Silverstein et al. *Am J of Sports Medicine*, 2007, Vol 35, No. 6). The effect of a single injection of HA on patients with symptomatic ankle (talo-crural) osteoarthritis show an improvement in VAS score of 44.5 points from baseline to 3 months (Witteveen A.G.H. et al. *I Foot and Ankle Surgery* 2008 *Vol* 14 p145-152).

The goal of this study is to demonstrate the clinical improvement and safety in patients treated with MONOVISC for shoulder osteoarthritis. Specifically, this study will provide confirmation to the effectiveness and safety of MONOVISC at relieving shoulder joint pain to 6 months post-treatment.

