6.5 Trial Design

This is a prospective, post market clinical follow-up (PMCF) multi-center, open-label study to evaluate the residual risk of injections of MONOVISC for relief of pain in patients with a diagnosis of an osteoarthritic shoulder joint.

The subjects in this study will be patients with a diagnosis of osteoarthritic (OA) joint who the investigator determines are appropriate candidates for treatment with a viscoelastic injection of MONOVISC.

Up to 25 subjects will be enrolled at up to 20 investigational sites in the EU. Subject participation will last approximately 6 Months, with visits scheduled at Screening, Baseline, 1 month, 3 month and 6 months.

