#### 2.0 Study Design

This is a prospective, post market clinical follow-up (PMCF) multi-center, open-label study to evaluate the residual risk of injections of MONOVISC for relief of pain in patients with a diagnosis of an osteoarthritic hip joint (MON 18-01), shoulder joint (MON 18-02), and ankle joint (MON 18-03).

The subjects in each of these study will be patients with a diagnosis of osteoarthritic (OA) joint who the investigator determines are appropriate candidates for treatment with a viscoelastic injection of MONOVISC.

In each study, up to 25 subjects will be enrolled at up to 20 investigational sites in the EU. Subject participation will last approximately 6 Months, with visits scheduled at Screening, Baseline, 1 month, 3 month and 6 months.

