#### 3.0 Objectives

The goal of these studies is to demonstrate the clinical improvement and safety in patients treated with MONOVISC for hip osteoarthritis, shoulder osteoarthritis, and ankle osteoarthritis. Specifically, this study will provide confirmation to the effectiveness and safety of MONOVISC at relieving the specified joint pain to 6 months post-treatment.

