#### 4.1.1Sample Size

The primary analysis will be the mean change in index joint pain from baseline to 6 months as measured by the Numerical Rating Scale.

The hypothesis to be tested is:

```
H_0: \mu_{DMON} = 0 versus H_A: \mu_{DMON} > 0.
```

In this hypothesis,  $\mu_{DMON}$  is the mean change in pain on walking from baseline at 6 Months in MONOVISC treated patients.

The data will be analyzed via a one sample t-test.

It is assumed that a mean change in pain from baseline of 2 points represents a clinically significant improvement with a standard deviation of 2 - 2.5 points, for 80% power and alpha of 5% then a total of 15 subjects are required. To ensure sufficient subjects are available at the 6 month follow up, it is proposed to enroll and treat at least 25 subjects which should be more than adequate to demonstrate that treatment of the study population with MONOVISC would reduce joint pain at 6 months.

Single sites should not enroll more than 50% of the total enrollment.

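### The study is meant to evaluate residual risk and confirm safety, but no adverse-event proportion gets a confidence limit; zero events in 25 treated subjects leaves a two-sided exact 95% upper limit of 13.7%

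*SAP*

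**What the plan says.** **The aim.** Protocol 6.5 calls this a "study to evaluate the residual risk of injections of MONOVISC for relief of pain", and SAP 2.0 repeats the description. Protocol 3 adds that "this study will provide confirmation to the effectiveness and safety of MONOVISC at relieving shoulder joint pain to 6 months post-treatment"; SAP 3.0 makes the same promise, and the objective in the Protocol synopsis also speaks of confirming safety.

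**The adverse-event analysis.** Protocol 9.2.2: "Subjects with AEs will be summarized with frequencies and percentages by system organ class and preferred term", and also by severity and relationship. SAP 4.4 plans frequencies and percentages of the events it defines as treatment-emergent, and then: "The number of subjects with at least one AE will be tabulated for each treatment group". It adds a Fisher's exact test between treatment groups, and counts of subjects and of events by severity, relationship, and local versus non-local site. Neither section names a confidence interval.

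**Intervals elsewhere.** SAP 4.1.3.4 plans exact 95% limits for the OMERACT-OARSI responder rate. SAP 4.1.3.5 and 4.1.3.6 plan 95% intervals for time to treatment failure and for medication use. SAP 4.2 sets the 5% level for tests and intervals in general but does not assign an interval to adverse events.

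**Sample size.** Protocol 9.1 and SAP 4.1.1 derive it from the t-test on NRS pain. On the number of subjects, SAP 2.0 says "In each study, up to 25 subjects will be enrolled at up to 20 investigational sites in the EU" while SAP 4.1.1 says "it is proposed to enroll and treat at least 25 subjects"; Protocol 6.5 and 9.1 differ in the same way.

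**The concern.** An observed proportion from about 25 subjects carries a lot of uncertainty, and the plan has no output that shows it on the safety side. A table entry of 0% or 4% under a stated aim of confirming safety gives the reader no sign of how large the true rate could still be. This matters most for the uncommon injection risks listed in Protocol 4.2, such as allergic reaction, infection and neurovascular damage. The Fisher's exact test does not fill the gap. MON 18-02 treats a single group, so the test has nothing to compare within it. If the groups were meant to be the three joints covered by the SAP, a test between joints would still put no bound on any event rate. The efficacy proportion gets exact limits and the safety proportions get none, although safety is one of the stated aims.

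**Working it through.** **1. What the sample size was built for.** Inputs from Protocol 9.1 and SAP 4.1.1: mean change 2, SD 2 to 2.5, power 80%, alpha 5%, stated n = 15. For a one-sample t-test with SD 2.5 and two-sided alpha 0.05, the noncentrality at n = 15 is (2/2.5) × √15 = 3.10, which gives power 0.821; 15 is the smallest n that reaches 80%. The stated figure is therefore reproduced at the upper SD. It is an efficacy calculation, and neither document gives a precision or a detectable rate for adverse events.

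**2. Upper limit when no event is seen.** The denominator is all treated subjects (Safety Population, Protocol 9.2.3 and SAP 4.5). The level is 95% (SAP 4.2). Sidedness is not stated and is taken as two-sided. The exact (Clopper-Pearson) upper limit for 0 of n is 1 − 0.025^(1/n).

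- n = 25: 1 − 0.025^(1/25) = 1 − 0.8628 = 13.7%
- n = 20 (an assumed shortfall): 1 − 0.025^(1/20) = 1 − 0.8316 = 16.8%
- n = 25, one-sided 95%: 1 − 0.05^(1/25) = 1 − 0.8871 = 11.3%

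**3. Limits for small counts.** With x events in 25, the lower limit is the 0.025 quantile of Beta(x, 26 − x) and the upper limit is the 0.975 quantile of Beta(x + 1, 25 − x).

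| Subjects with event | Observed | Two-sided exact 95% CI |
|---|---|---|
| 0/25 | 0% | 0% to 13.7% |
| 1/25 | 4% | 0.1% to 20.4% |
| 2/25 | 8% | 1.0% to 26.0% |
| 3/25 | 12% | 2.5% to 31.2% |
| 5/25 | 20% | 6.8% to 40.7% |

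**4. Chance of seeing nothing.** With true rate p, the probability of no case in 25 is (1 − p)^25.

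- p = 1%: 77.8%
- p = 2%: 60.3%
- p = 5%: 27.7%
- p = 10%: 7.2%, so at least one case is seen with probability 92.8%

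The study would probably reveal a common problem. An event with a true rate of 2% would more likely than not go unseen.

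**5. Can intervals be computed from the plan as written?** Only after two differences are settled. Protocol 9.2.2 counts a subject with repeated episodes once, at the worst grade and the closest relationship, whereas SAP 4.4 includes every reported event. Protocol 9.2.2 classifies relationship to product or procedure, whereas SAP 4.4 classifies relationship to CTM. A binomial interval needs one count per subject and one definition of related.

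**The case against.** The best defence is that descriptive adverse-event tables are ordinary in a small post-market follow-up. The safety endpoint (Protocol 6.4, SAP 3.0) is the collection of incidence, severity and relationship. No threshold or success rule depends on it. Protocol 8.1.2 requires serious events to be reported within 24 hours whatever their relationship, and Protocol 13.16 places the wider risk judgement in an ongoing risk analysis built on existing knowledge. Subject counts and a defined Safety Population will be reported, so a reader could work out an exact interval for the overall any-AE proportion.

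Much of this stands. It shows that the sample size needs no defence on safety grounds and that no decision in the plan goes wrong. It does not justify announcing that safety will be confirmed while planning no measure of precision. For related events, the reader's own calculation also depends on which of the two counting rules was used.

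Three stronger readings are tempting, and the documents do not support them. A reader might infer that counts and percentages are the only adverse-event output; SAP 4.4 does also name the Fisher's exact test, even though it has no use within this study. A reader might infer that the trial fails to answer its safety question; evaluating residual risk can be done by estimation, and the study can do that. A reader might also want one round cut-off below which nothing can be excluded; the two-sided limit is about 1 in 7 and the one-sided about 1 in 9 at 25 subjects with no events, and both move with the number treated and the number of events.

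**Conclusion.** The point holds as a gap between the stated aim and the planned output. Two-sided exact 95% limits reach 13.7% with no events in 25 and 20.4% with one, so the data can estimate risk but cannot confirm safety for uncommon events. The figures assume that subjects are independent, that 25 are treated and that intervals are two-sided. Because the documents say both up to and at least 25, the number treated could be lower, and 20 treated would raise the zero-event limit to 16.8%. The primary pain analysis is not affected, and nothing here calls for a larger sample. It is a low-cost change that should be made because it alters what the report can properly say about one of the study's own aims.

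**What to change.** - **SAP 4.4:** add two-sided exact (Clopper-Pearson) 95% confidence intervals on the Safety Population, counting each subject once, for the proportions with any AE, any treatment-related AE, any local injection-site AE and any SAE. PROC FREQ with the BINOMIAL option, already specified in SAP 4.1.3.4, produces them.
- **Before that:** reconcile Protocol 9.2.2 and SAP 4.4 on the definition of relationship (product or procedure versus CTM) and on repeated episodes (worst once versus all events). Event counts can still be tabulated separately.
- **Protocol 3, 6.5 and 9.1 and SAP 3.0:** restate the safety aim as estimation. Give the zero-event upper limit as 1 − 0.025^(1/n), with n the number actually treated, and 13.7% as the value at n = 25.
- **Optional:** a pooled table across the three studies. If each treated 25, 0/75 would give 1 − 0.025^(1/75) = 4.8%, but the SAP specifies no such pooling and the fix does not need it.

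The cost is a SAP paragraph, a few table columns and small wording changes in the Protocol. Enrolment, visits and data collection stay as they are. The downside is a safety statement that reads less favourably.
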